5.3 Handling of Dropouts and Missing Data

Every effort will be made to minimize the number of dropouts and to document reasons for dropping out. The following rules will be followed for missing leg activity monitoring data:

- Missing daily values within a 2-week period will be imputed as the mean of the non-missing daily values for the period.
- If a subject is missing all values for a 2-week post-baseline period and has not discontinued the study, the Last-Observation-Carried-Forward (LOCF) method will be used to impute the value for the 2-week period.

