9.6 Visit 5: Follow-Up Period (Week 1, Study Day 8 ± 1)

The following will be performed:

- Vital Signs
- Hematology
- Serum Chemistry
- Physical Therapy Instruction and Subject Exercise Diary given to Subject
 - Leg Activity Monitor data download (applicable for US and Japan only)
- Blood draw for Serum anti-HLA Antibodies
- Blood draw for PBMC
- Head MRI with Gadolinium (MRI must be read before re-starting any antiplatelet, anticoagulant, or non- steroidal anti-inflammatory agents)
- Adverse Events
- Concomitant Medications

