3.0 STUDY DESIGN

3.1 Overview

This is a double-blind, sham surgery controlled study of stereotactic, intracranial injection of SB623 cells in patients with fixed motor deficits from TBI. The study will be conducted at approximately 30 sites in North America (i.e., United States), Eastern Europe (i.e., Ukraine), and Asia Pacific (i.e., Japan).

Table 1 in the main SAP lists the procedures to be followed throughout the course of the study. Activity data will be downloaded at the clinical site and changes from Baseline in activity parameters will be calculated at Days 28, 84, 168, 252, and 336.

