5.0 STATISTICAL CONSIDERATIONS

5.1 General Methodology

The statistical analysis of the data will be performed using SAS[®] version 9.4 or higher. All statistical tests will be performed at the 0.05 significance level.

Leg activity monitoring variables will be documented using summary tables, subject data listings, and summary figures. Continuous variables will be summarized using descriptive statistics, specifically the number of observations, mean, median, standard deviation, minimum and maximum. Categorical variables will be summarized by frequencies and percentages. For the most part results will be presented for the four treatment groups separately and the three SB623 dose groups pooled. The three SB623 dose groups will be pooled for all statistical tests comparing SB623 to sham surgery, except where noted otherwise (i.e., dose response analyses).

Data listings will be sorted by treatment group and subject ID. All date fields will be presented in a format of ddmmyyyy (i.e., 01Jan2018) in the listings.

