7.0 EFFICACY ANALYSES

In this SAP, the following variables from Leg Activity Monitoring will be analyzed.

- Average Daily Total Energy Expenditure (affected side and non-affected side separately)
- Average Daily Activity Counts (affected side and non-affected side separately)
- Average Non-Sedentary Time per Day (affected side)
- Average Time of Moderate or Vigorous Activity per Day (affected side)

For the first two endpoints listed above, the value of the endpoint will be calculated as follows. The mean of each day's value will be calculated for the two-week period prior to Baseline, which will be the baseline value for this endpoint, and for the two-week period prior to each study visit.

Average Non-Sedentary Time per Day: The leg activity monitor can measure the time in minutes within each activity range. Activity range is categorized as sedentary, light, moderate, or vigorous based on energy expenditure. The light, moderate, and vigorous activity ranges are considered non-sedentary. The mean of each day's time within the non-sedentary range will then be obtained for the two-week period prior to Baseline, which will be the baseline value for this endpoint, and for the two-week period prior to each study visit.

Average Time of Moderate or Vigorous Activity per Day: The leg activity monitor can measure the total amount of time in minutes within the moderate or vigorous activity ranges throughout each day. The mean of each day's value will then be calculated for the two-week period prior to Baseline, which will be the baseline value for this endpoint, and for the two-week period prior to each study visit.

For the pooled SB623 and sham surgery treatment groups, descriptive statistics will be presented by visit for the actual values and the changes from baseline for each leg activity monitoring variable. The difference between treatment groups (pooled SB623 - sham surgery) in the mean change from baseline will also be presented. For each leg activity monitoring variable, the one-sample t-test will be used to test whether the mean change from baseline equals 0 for each post-baseline time point for each treatment group. Two-sided, two-sample t-tests will be used to test whether the mean changes from baseline are equal for the two treatments (pooled SB623 vs. sham surgery). Analyses will be performed overall and for the subgroups specified in Section 5.6.

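### The leg-activity SAP fills wholly unworn 2-week periods by LOCF and tests them as observed, without an observed-only analysis; the bias can go either way and affects an exploratory endpoint only.

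*SAP*

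**What the plan says.** SAP Appendix F, section 5.3, has two rules for missing monitor data.

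- Partly worn window: "Missing daily values within a 2-week period will be imputed as the mean of the non-missing daily values for the period". This only averages the days that were worn.
- Wholly unworn window: "If a subject is missing all values for a 2-week post-baseline period and has not discontinued the study", then "the Last-Observation-Carried-Forward (LOCF) method will be used to impute the value for the 2-week period". Subjects who have left the study are not filled in.

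Section 7.0 takes as baseline the daily mean over "the two-week period prior to Baseline, which will be the baseline value for this endpoint", and uses the two weeks before each study visit afterwards. Under section 3.1, "changes from Baseline in activity parameters will be calculated at Days 28, 84, 168, 252, and 336". The analyses are one-sample t-tests within group, a between-group comparison ("Two-sided, two-sample t-tests will be used to test whether the mean changes from baseline are equal for the two treatments"), and linear regressions on dose. Section 5.1 adds: "All statistical tests will be performed at the 0.05 significance level". Section 5.2 adjusts for no covariates.

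The protocol also schedules a monitor download at Visit 5, Day 8 (section 9.6: "Leg Activity Monitor data download (applicable for US and Japan only"). Protocol section 15.10 makes the monitor mandatory in the US and Japan only. Both documents list lower-limb motion among the exploratory endpoints.

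**The concern.** An unworn or dead ankle sensor carries no information that leg activity stayed where it was, yet the rule turns it into a data point that says so. Appendix F does not flag imputed values, does not limit how long a value may be carried, and plans no analysis of observed periods alone. The integrated output list has 21 leg-activity tables (14.2.32.1 to 14.2.37.4) and two figures (14.2.23.1 and 14.2.23.2). None is titled as a sensitivity analysis.

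The rule also departs from the rest of the plan. The protocol's primary analysis (18.2.2.1) and the genotyping (7.0), antibody (7.0) and head MRI (7.1) SAPs all leave missing observations unimputed. LOCF in the main SAP (5.3) is written for individual FMMS items.

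At stake are the estimated differences, the t-test p-values and the dose slopes for the leg-activity variables.

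**Working it through.** **The plan's own figure.** The only planning figures are for FMMS (main SAP 3.4): difference 10.0 − 3.0 = 7.0, SD 7.25, two-sided 0.05, 80% power, 3:1. Controls needed = (1 + 1/3) × (1.960 + 0.842)² × 7.25² / 7.0² = 11.2, so 12, and 48 in total. Power by noncentral t at 36:12 is 0.81. Then 48 × 1.08 = 51.8, about 52. The figure reproduces, but it is not a leg-activity figure.

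**Assumptions, none of them in the documents for this endpoint.**
- FMMS values stand in for leg activity.
- The sample is 39:13, all 52 subjects. This is an upper limit because of the US/Japan restriction.
- Change grows linearly from Baseline to Week 24 (Day 168).
- SD is 7.25 at each visit, with correlation 0.7 between visits.
- A share m of each arm stops wearing the monitor, evenly spread over the three windows to Week 24 and unrelated to outcome.
- Baseline is carried if no later value exists.

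**Expected Week 24 result.** Subjects who stop before Day 28, Day 84 or Day 168 carry 0, 28/168 or 84/168 of the Week 24 change. The average is (0 + 1/6 + 1/2)/3 = 2/9. An arm with true change c then shows c × (1 − 7m/9).

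- m = 20% in both arms: 7.0 × (1 − 0.156) = 5.9.
- m = 30% in both arms: 7.0 × (1 − 0.233) = 5.4.

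**Which value is carried.** If a Day 8 value were carried instead of Baseline, the average becomes (8/168 + 1/6 + 1/2)/3 = 0.238. The 20% case gives 7.0 × (1 − 0.2 × 0.762) = 5.9 again. At Day 28 itself the choice decides whether the imputed change is exactly 0.

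**False difference.** If both arms truly change by c, the expected difference is c × (7/9) × (m in control − m in SB623). With c = 8 and non-wear of 10% on SB623 and 40% on control, this is 8 × 0.778 × 0.30 = 1.9. With 10% and 20% it is 0.6.

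**Waning effect.** If the true difference is D1 at the last worn visit and D2 now, a share m carrying forward gives D2 + m × (D1 − D2). That is too large whenever D1 exceeds D2.

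**Simulated rejection rates** (two-sided equal-variance t-test, Week 24, 39:13):

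| Setting | LOCF | Observed only |
|---|---|---|
| Power, true 7.0, 20% non-wear in both arms | 67% | 74% |
| Power, true 7.0, 30% non-wear in both arms | 59% | 68% |
| Type I, both arms +8, non-wear 10% vs 20% | about 6% | about 5% |
| Type I, both arms +3, non-wear 10% vs 40% | about 6% | about 5% |
| Type I, both arms +8, non-wear 10% vs 40% | about 13% | about 5% |

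With equal non-wear of 20% and both arms at +8, type I error under LOCF stays near 5%. At an illustrative 24:8, the last row of the table falls to about 10%.

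**The case against.** The strongest reply is that the matter is small and its size unknown. The endpoint is one of 13 exploratory items, collected in a regional subset and tested without multiplicity control. The borrowed inputs are FMMS points, whereas the leg variables are energy expenditure, activity counts and minutes. Monitors may be replaced at any visit when the battery is low. The listings of daily values and of monitor reapplication would let a reader find unworn periods. All of this stands and sets the priority. It does not supply an observed-only analysis.

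Several stronger readings are tempting but not supported.

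- *Every imputed first-visit change is exactly 0, and a subject who stops at once scores 0 at all five visits.* Section 5.3 does not say which value is carried. Day 8 data are downloaded, and section 7.0 speaks of each study visit. A two-week window before Day 8 would straddle surgery, so that reading has its own problem, but the text does not exclude it.
- *LOCF always dilutes.* That holds for an effect that grows; a waning effect is overstated.
- *The full 7.0 is cut by a fifth already at the first visit.* Under linear growth the true Day 28 difference is 7.0 × 28/168 = 1.2. Carrying Baseline for 20% makes it 0.9.
- *Type I error is about 13%.* This needs a 10% versus 40% wear gap in a double-blind trial and both arms improving by 8, when the plan assumes 3.0 for sham in FMMS. Nothing in the documents suggests that wear would differ by arm.
- *Restricting LOCF to subjects who have not discontinued is itself a defect.* The restriction limits how far the rule reaches.

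**Conclusion.** The point holds in a limited form. The plan carries forward whole unworn windows for subjects still in the study, tests them as measured, and offers no check on observed periods. It also leaves open which value is carried. The direction of bias depends on the time course, and a false difference requires non-wear that differs by arm, or is related to outcome, together with real change over time.

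The size in this trial cannot be determined from the documents. Under the borrowed values, LOCF loses about 1.1 to 1.6 points of a Week 24 difference of 7.0 and 7 to 9 percentage points of power relative to observed-only testing. Type I error is barely raised under modest wear gaps. Observed-only testing keeps its nominal level here because stopping was assumed unrelated to outcome; it would not remove bias if non-wear tracked leg function.

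A reader might infer that the trial's efficacy conclusion is at risk. It is not: no primary or secondary endpoint uses this rule. Priority is low.

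**What to change.** In SAP Appendix F, section 5.3:

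1. Remove whole-period LOCF as the main rule and leave unworn 2-week periods missing. The rule for partly worn windows can stay.
2. Run the planned t-tests and dose regressions in section 7.0 on observed periods. A repeated-measures model over the five visits is optional. An unstructured covariance has 15 parameters at five visits, so name a simpler structure in case it does not converge in this small subset.
3. Keep LOCF as a labelled sensitivity run, and state whether Baseline or a Day 8 value may be carried.
4. Report observed and imputed periods by arm and visit.

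The SAP addendum records that post-hoc analyses were added after the interim results were unblinded. If the change comes after that point, the report should show both versions and label the change as such.

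Cost: one SAP bullet, a rerun of existing programs, one count table, and a slightly smaller n per visit. No new data are needed.

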5.4 Multicenter Study

Approximately 52 subjects will be randomized into the study at approximately thirty (30) sites in North America (i.e., United States), Eastern Europe (i.e., Ukraine), and Asia Pacific (i.e., Japan). A maximum of 12 subjects will be enrolled at each Assessment site, and a maximum of 16 subjects will be enrolled or treated at each Surgery or Comprehensive site, respectively.

5.5 Multiple Comparisons / Multiplicity

Multiplicity considerations will not be taken into consideration in the analyses for this Phase 2 study.

5.6 Examination of Subgroups

The analyses of the leg activity monitoring variables for the affected side will be performed on the following subgroup of interest:

- Lower extremity deficit patients (lower extremity deficit patients are those patients with a Motricity LE Scale score at Screening of 10-78)

6.0 ANALYSIS POPULATIONS

6.1 Modified Intent-to-Treat Population

The Intent-to-Treat (ITT) population will include all randomized patients. All efficacy analyses will be conducted on modified ITT (mITT) population, which is defined as all randomized patients who complete the surgical procedure. In analyses based on the mITT population, subjects will be analyzed according to their randomized treatment assignment. Analyses based on the mITT population will be considered the primary analyses of efficacy.

6.2 Per Protocol Population

The Per Protocol (PP) population will include all randomized patients who have no major protocol violations. Major protocol violations will be identified based on blinded data after the study is completed, but before database lock and the unblinding of the treatment group assignments. All efficacy analyses will be repeated on this population. In analyses based on the PP population, subjects will be analyzed according to their randomized treatment assignment. Analyses based on the PP population will be considered secondary analyses of efficacy.

7.0 EFFICACY ANALYSES

In this SAP, the following variables from Leg Activity Monitoring will be analyzed.

- Average Daily Total Energy Expenditure (affected side and non-affected side separately)
- Average Daily Activity Counts (affected side and non-affected side separately)
- Average Non-Sedentary Time per Day (affected side)
- Average Time of Moderate or Vigorous Activity per Day (affected side)

For the first two endpoints listed above, the value of the endpoint will be calculated as follows. The mean of each day's value will be calculated for the two-week period prior to Baseline, which will be the baseline value for this endpoint, and for the two-week period prior to each study visit.

Average Non-Sedentary Time per Day: The leg activity monitor can measure the time in minutes within each activity range. Activity range is categorized as sedentary, light, moderate, or vigorous based on energy expenditure. The light, moderate, and vigorous activity ranges are considered non-sedentary. The mean of each day's time within the non-sedentary range will then be obtained for the two-week period prior to Baseline, which will be the baseline value for this endpoint, and for the two-week period prior to each study visit.

Average Time of Moderate or Vigorous Activity per Day: The leg activity monitor can measure the total amount of time in minutes within the moderate or vigorous activity ranges throughout each day. The mean of each day's value will then be calculated for the two-week period prior to Baseline, which will be the baseline value for this endpoint, and for the two-week period prior to each study visit.

For the pooled SB623 and sham surgery treatment groups, descriptive statistics will be presented by visit for the actual values and the changes from baseline for each leg activity monitoring variable. The difference between treatment groups (pooled SB623 - sham surgery) in the mean change from baseline will also be presented. For each leg activity monitoring variable, the one-sample t-test will be used to test whether the mean change from baseline equals 0 for each post-baseline time point for each treatment group. Two-sided, two-sample t-tests will be used to test whether the mean changes from baseline are equal for the two treatments (pooled SB623 vs. sham surgery). Analyses will be performed overall and for the subgroups specified in Section 5.6.

In addition, each leg activity monitoring variable will be analyzed to examine dose response. For each leg activity monitoring variable and SB623 dose group (2.5 million SB623 cells, 5 million SB623 cells, 10 million SB623 cells), a two-sided, one-sample t-test will be used to test whether the mean change from baseline equals 0 for each post-baseline time point. Linear regression analyses with a term for dose will be used to test the null hypothesis that the coefficient of dose equals 0. Dose will be treated as a continuous variable, and the control treatment will not be included in this analysis. The p-value for the test of the null hypothesis that the coefficient of SB623 dose equals 0 will be presented.

Analyses will be performed overall and for the subgroup specified in Section 5.6.

Graphs will be presented summarizing the mean change from baseline in the Average Daily Activity Count (affected side and non-affected side separately) over time by treatment group (pooled SB623 and control) for both the mITT and Per Protocol populations. The graphs will plot

the mean changes (\pm standard error) over time, as well as the p-value at each timepoint from a two-sided, two-sample t-test testing the null hypothesis that the true mean change is equal for the two treatments.

1.0 INTRODUCTION

The purpose of this addendum to the Statistical Analysis Plan for the TBI-01 main study is to (1) provide the justification for imputation of the baseline FMMS score for one patient and (2) to document that the CSR will include additional reporting due to post-hoc analyses.

2.0 JUSTIFICATION FOR IMPUTATION OF THE BASELINE FMMS SCORE FOR ONE PATIENT

For one subject in the mITT population, the baseline FMMS evaluation was performed on the incorrect side. The baseline FMMS score is required in order to calculate change from baseline in the FMMS score at Week 24, the primary study endpoint. There is no data handling convention specified for this situation in the Statistical Analysis Plan. As a post-hoc solution, the baseline value for this subject was imputed as defined below.

The initial step in the imputation was to identify baseline variables that measure the severity of TBI. The variables selected were the Motricity Index (MI) scores (upper and lower) and the baseline Glasgow Outcome Scale - Extended (GOS-E) score. The MI is used to measure strength in the upper and lower extremities after stroke, with the upper and lower scores evaluated on the affected side. The GOS-E score measures the level of disability. For subjects in the mITT population with non-missing baseline FMMS scores, the relationship between these variables and the baseline FMMS score was estimated by performing a linear regression (SAS PROC GLM), with the baseline FMMS score as the dependent variable and the MI and GOS-E scores as independent variables. The parameter estimates obtained from the linear regression were then applied to the subject missing a baseline FMMS evaluation in order to impute a baseline FMMS value. This imputed value was used in the analysis.

A sensitivity analysis on this result was then performed by removing the imputed baseline FMMS value from the primary endpoint analysis. By removing this imputed value, this subject was excluded from the sensitivity analysis.

Since the baseline FMMS evaluation on the correct side was missing, the choice was either to impute the missing value or to exclude the subject from this analysis. As the intent of analyses based on the mITT population is to include all randomized subjects who completed the surgical procedure, the primary analysis was based on imputing this value, but, as described above, a sensitivity analysis was performed with this subject excluded.

3.0 EXPANDED STUDY REPORTING FOR POST-HOC ANALYSES

Some post-hoc analyses were added after unblinding of the results of the interim analysis. The tables and figures presenting the results of these post-hoc analyses will be included in the CSR: these analyses will be numbered as 12.x.x.
